9.7.1.4 Interim analyses

NA

9.7.1.5 Other topics

NA

9.7.2 Determination of sample size

The sample size of 116 completed patients is calculated based on the primary efficacy variable, change from baseline in mean systolic blood pressure, and a standard deviation of 11 mmHg (based on previous data) is used. The sample size is calculated to ensure at least 80% power to detect statistical significance for the comparison valsartan 0.25 mg/kg versus valsartan 4 mg/kg under the alternative hypothesis that the treatment difference is 6 mmHg at a two-sided significance level of 0.05. Assuming 10% drop-out rate, the total targeted sample size to be randomized is 130 patients.

10 Clinical Study Report - Appendix 16.1.9 Documentation of statistical methods

10.1 Introduction

This appendix gives details about statistical methods in addition to the report text. All analyses will be performed using SAS Version 9.4 in a UNIX environment.

10.2 Definition of pooled centers for efficacy analysis

Due to small sample size at most individual study centers, data from centers within a geographic region will be pooled for the efficacy analysis. Center pooling will be pre-defined prior to the database lock and used in the efficacy analyses. If one or two particular centers

have substantially larger enrollment than other centers in one geographic area, the “super center” may be left as one group by itself.

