6.2 Patient demographics/other baseline characteristics

Patient demographic and baseline characteristic data to be collected on all patients include date of birth, sex, race and ethnicity, height, weight, and head circumference.

Relevant medical history/current medical condition data includes data until the start of study drug. Where possible, diagnoses, and not symptoms will be recorded. Patients with CKD as defined in [Section 4](#) should have a corresponding medical history of chronic kidney disease etiology recorded.

Visit 1

At Visit 1, the investigator or investigator's staff will call into IRT and register the patient. During this call, the patient's date of birth, gender, CKD status, and body weight will be entered into the IRT, along with the patient number.

Visit 2

The patient is enrolled into the trial at Visit 2 once all eligibility criteria are met (within 28 days of Visit 1). At this visit, the investigator or investigator's staff will call into IRT and enter the patient's body weight and CKD status.

CKD status, age and region

At Visit 2, the investigator or staff will also enter the patient's CKD status (CKD or non-CKD patient). The CKD definition is discussed in [Section 4](#). At least 50% of the patients enrolled into the trial must have CKD. IRT will be used to track CKD status at Visit 2. IRT will be used to prevent over enrollment of non-CKD patients, in order to ensure that a sufficient number of CKD patients are enrolled (e.g. should enrollment of 65 non-CKD patients be achieved, IRT will not permit enrollment and assignment of study drug to further non-CKD patients in the study). Patients will be stratified by CKD status.

Visit 2 to Visit 10

The IRT system will be called at every visit. Study medication number assignment will be at every dispensing visit (Visit 2-Visit 10). The dose of medication that the patient receives will be based on the patient's weight at Visit 2 for double blind, and at Visit 5 and Visit 8 during the open-label phase.

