9.4.2 Statistical model, hypothesis, and method of analysis

The null hypothesis is that there is no treatment difference in the reduction of MSBP between dose groups 0.25mg/kg and 4 mg/kg. The alternative hypothesis is that there is a difference between dose groups 0.25 mg/kg and 4 mg/kg.

The comparison will be tested at a two-sided significance level of 0.05. The change from baseline in MSBP at Week 6 endpoint during double-blind period will be analyzed using an analysis of covariance model (ANCOVA) with treatment and CKD strata as factors and baseline MSBP as a covariate for the FAS population.

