9.7 Statistical methods planned in the protocol and determination of sample size

Data will be analyzed by according to the data analysis section 9 of the study protocol that is available in [Appendix 16.1.1 of the CSR](#). Important information is given in the following sections and details are provided, as applicable, in [Appendix 16.1.9 of the CSR](#).

An overview of the study design is presented in the following figure:

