9.7.1.2 Efficacy evaluation

9.7.1.2.1 Analysis of the primary variable(s)

The primary objective is to evaluate if a dose dependent reduction in MSBP exists when comparing two doses of valsartan solution (0.25 mg/kg and 4 mg/kg) over a 6 week period in children 1-5 years old with hypertension (MSBP \geq 95th percentile for age, gender and height), with or without CKD.

The primary efficacy variable is change from baseline (Visit 2) in mean systolic blood pressure (MSBP) at Week 6 endpoint during the double-blind period 1. The primary analysis will be performed on the FAS.

Statistical hypothesis, model, and method of analysis

The null hypothesis is that there is no treatment difference in the reduction of MSBP (mmHg) between dose groups 0.25mg/kg (low) and 4 mg/kg (high). The alternative hypothesis is that there is a difference between dose groups 0.25 mg/kg and 4 mg/kg. The hypotheses were expressed as follows:

$$H_0: \delta_{\text{low}} = \delta_{\text{high}} \text{ versus } H_1: \delta_{\text{low}} \neq \delta_{\text{high}}$$

where δ s are the mean changes from baseline at Week 6 endpoint in MSBP in the treatment group indicated.

The treatment comparison will be tested at a two-sided significance level of 0.05. The change from baseline in MSBP at Week 6 endpoint during double-blind phase will be analyzed in the FAS using an analysis of covariance model (ANCOVA) as the primary analysis model with treatment and CKD strata as factors and baseline MSBP as the covariate. The baseline MSBP values will be centered by subtracting the overall mean of all patients included in the analysis for FAS. For patients with missing values at Week 6, the last post-baseline observation during the double-blind period will be carried forward (LOCF) as the Week 6 endpoint. CKD strata (yes/no) are the stratification factor used for IRT randomization. When the investigator entered a wrong stratification stratum in IRT, a protocol deviation (PD code = S01) is registered and the correct stratification factor is used for all analyses. The estimated treatment difference for the treatment comparison will be tabulated along with the associated 95% confidence interval and two-sided p-value. Treatment by baseline MSBP interaction will be examined by adding the treatment-by-baseline-MSBP term to the primary analysis model. The results of this assessment will be presented in the CSR section 16.1.9.

Supportive analyses

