Percentage of patients achieving MSBP < 95th percentile for age, gender and height at Week 6 endpoint will be also analyzed using a logistic regression model with treatment and CKD strata as factors and baseline MSBP as the covariate. The odds ratio of Valsartan 4.0 mg/kg / Valsartan 0.25 mg/kg will be computed, along with the associated 95% confidence interval and p-value. In addition, the number (and %) of patients achieving MSBP < 95th percentile for age, gender and height will be summarized by treatment and visit (including the Week 6 endpoint). Similar analyses will be carried out for the CKD and non-CKD subgroups of patients.

Percentage of patients achieving both MSBP and MDBP < 90th percentile for age, gender and height; percentage of patients achieving both MSBP and MDBP < 95th percentile for age, gender and heights.

Percentage of patients achieving both MSBP and MDBP < 90th percentile for age, gender and height at Week 6 endpoint will be analyzed using a logistic regression model with treatment and CKD strata as factors and baseline MSBP as the covariate. The odds ratio of Valsartan 4.0 mg/kg / Valsartan 0.25 mg/kg will be computed, along with the associated 95% confidence interval and p-value. In addition, the number (and %) of patients achieving both MSBP and MDBP < 90th percentile for age, gender and height will be summarized by treatment and visit (including the Week 6 endpoint). Similar analyses will be carried out for the CKD and non-CKD subgroups of patients.

Similar analyses will be also performed for the percentage of patients achieving both MSBP and MDBP < 95th percentile for age, gender and height at Week 6 endpoint.

UACR (Urine Albumin Creatinine Ratio) in CKD patients

UACR was collected for CKD patients only. The UACR value at a given visit for a patient is to be derived by the median of the three lab values collected for that visit. The UACR value will be assessed in the CKD patients.

Change from baseline in log(base 10)-transformed UACR will be analyzed using an ANCOVA model with treatment as a factor and log (base 10)-transformed baseline UACR as a covariate. The estimated treatment effects, treatment difference, 95% confidence interval, and p-value for the treatment comparison will be provided. The estimates to be presented will be in back-transformed scale.

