10.3 Sample SAS program for efficacy analyses

The SAS code provided is intended to reflect the type of analyses planned; however, the actual code used may not be a verbatim of this example. The variable names used in this code were selected for understanding of the methodology and do not necessarily reflect the actual variable names in the data.

ANCOVA model for primary analysis

For the ANCOVA model in the analysis of change from baseline in MSBP at Week 6, the following SAS code are used:

```
PROC MIXED DATA=eff;
  CLASS treatment CKD;
  WHERE population = population (FAS);
  MODEL response= treatment CKD baseline_MSBP;
  ESTIMATE 'Valsartan High dose vs. Valsartan Low dose' treatment 1 -1/CL;
  run;
```

- “eff” denotes the efficacy data set containing individual observations for the change from baseline in MSBP
- “treatment” denotes the variable containing the treatment groups (Low, High)
- “CKD” denotes the variable containing the CKD strata (CKD and non-CKD)
- “baseline_MSBP” denotes the centered baseline variable containing individual patient baseline MSBP deviation from the mean of all FAS patients.

Logistic regression model

The SAS procedure MIXED is used with the following SAS code:

```
proc logistic data=eff;
  class treatment CKD/(param=ref ref='Low');
  model response = trt base;
  contrast 'High dose vs. Low dose' treatment 1 -1 / estimate=exp;
run;
```

where `y`, `region`, `trt`, and `base` denote control or response variable, region, treatment, and baseline value (msSBP, or msDBP for `y` involving only msDBP) respectively.

The odds ratio of High dose /Low dose will be computed, along with associated 95% confidence intervals.

Comparability of baseline characteristics

Baseline comparability between the three treatment groups, for continuous parameters, was tested using two-sample t-test:

```
proc ttest;  
  class treatment;  
  variable <Quantitative baseline variable>;  
run;
```

Baseline comparability between treatment groups, for categorical parameters, was tested using a CMH chi square-test:

```
proc freq ;  
  tables treatment* <Qualitative baseline variable > / cmh noprint;  
  output out=<output dataset> cmhga;  
run;
```

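### Do the centre pooling with no assigned role (SAP 10.2) and the sample logistic code without the CKD term leave the efficacy models undefined?

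*SAP*

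**What the plan says.** SAP 10.2 groups centres by geographic region because most are small, lets an unusually large centre stand alone, and adds: "Center pooling will be pre-defined prior to the database lock and used in the efficacy analyses". SAP 10.1 describes the appendix containing 10.2 in these terms: "This appendix gives details about statistical methods in addition to the report text".

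The primary model is set elsewhere. SAP 9.7 defers to the protocol: "Data will be analyzed by according to the data analysis section 9 of the study protocol"; appendix details are to be given only as applicable. Protocol 9.4.2 specifies an ANCOVA "with treatment and CKD strata as factors and baseline MSBP as a covariate for the FAS population". SAP 9.7.1.2.1 repeats this "as the primary analysis model with treatment and CKD strata as factors and baseline MSBP as the covariate". The PROC MIXED example in SAP 10.3 has the same three terms.

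For the secondary responder endpoints, SAP 9.7.1.2.2 says of MSBP below the 95th percentile that it "will be also analyzed using a logistic regression model with treatment and CKD strata as factors and baseline MSBP as the covariate". It gives the same model for MSBP below the 90th percentile and for MSBP and MDBP both below the 90th, and calls for similar analyses for both below the 95th. The matching code in SAP 10.3 is introduced with "The SAS procedure MIXED is used with the following SAS code" but is a PROC LOGISTIC step. It lists CKD in CLASS, has only `trt` and `base` in MODEL, and is followed by a legend that defines an unused `region`.

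**The concern.** Section 10.2 reads as a commitment, and an appendix that adds to the report text could be taken to add a region term to the efficacy models. It does not say which endpoints would be affected, or whether the adjusted model would be primary or supportive. If that stayed open until after unblinding, one could ask which model had been planned, and the two models can fall on opposite sides of p = 0.05. The protocol also has a heading in section 6.2, "CKD status, age and region", which hints that region was once meant to be a design factor.

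The logistic code raises a different risk. CKD status is the randomisation stratification factor. A programmer who followed the code rather than the text would drop it from four secondary analyses, pull the odds ratio toward 1 and lose some power.

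**Working it through.** **1. Is the primary model in doubt?** Treatment, CKD strata and baseline MSBP appear in the protocol synopsis (data analysis), protocol 9.4, protocol 9.4.2, SAP 9.7.1.2.1 and the PROC MIXED code in SAP 10.3. That is five statements without a difference in terms, and SAP 9.7.1.2.1 calls this the primary analysis model.

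**2. Does any other efficacy model use region?**

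| Analysis | Terms |
|---|---|
| Dose slope (SAP 9.7.1.2.1) | CKD, baseline MSBP, dose per kg |
| Interaction checks | primary model plus treatment-by-baseline or treatment-by-CKD |
| MDBP | treatment, CKD, baseline MDBP |
| Blood pressure responders | treatment, CKD, baseline MSBP |
| UACR change and response, cystatin C GFR (CKD patients only) | treatment, baseline |
| Period 2 | descriptive, no region breakdown |

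None does. Under the heading in protocol 6.2, the text stratifies on CKD only.

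**3. Does the design rely on region?** Inputs from protocol 9.7 and SAP 9.7.2: difference 6 mmHg, SD 11, two-sided 0.05, 80% power.
- Per arm: 2 × (1.960 + 0.842)² × 11² / 6² = 52.8, so 53 per arm and 106 in total.
- With the planned 116 (58 per arm): SE = 11 × √(2/58) = 2.04; 6/2.04 = 2.94; power = Φ(2.94 − 1.96) = 83.6%, or 83.0% with the t distribution. This fits the stated minimum of 80%.
- 116/0.9 = 128.9, so 129; the plan uses 130.

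Region plays no part here. Adding it costs almost nothing in degrees of freedom: 116 − 4 = 112 residual without it and 105 with eight pools, and power is 82.9% in both cases.

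**4. What if region were added?** Simulation at the same inputs, 8,000 trials per scenario, with 3, 5 or 8 pools and a between-region SD of 0, 2 or 4 mmHg. The documents give neither figure, so both are assumptions.
- Type I error: 4.4-5.4% for either fixed model (Monte Carlo SE 0.24 points).
- Power: 82-83% without region, 80-87% with it.
- Opposite verdicts at 0.05 under the 6 mmHg difference: 2.4% of trials (3 pools, SD 0) to 8.7% (8 pools, SD 4). Repeats with other assumed region sizes gave 2.5% and 2.9% at the low end, and 7.6% and 7.7% at the high end. In one of these repeats the null was also run, and the figures there were 0.9% and 3.6%.

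Some disagreement appears even when region has no effect at all, as it would with any added covariate, so it does not measure harm.

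**5. What if CKD were left out of the responder model?** Worked example with assumed values: conditional treatment odds ratio 2.5, low-dose response 40% in non-CKD patients, half the patients with CKD, CKD odds ratio 0.5.
- Non-CKD: odds 0.667 and 1.667, so response 0.400 and 0.625.
- CKD: odds 0.333 and 0.833, so response 0.250 and 0.4545.
- Averages: 0.325 and 0.540. Odds ratio without CKD = (0.540/0.460) / (0.325/0.675) = 2.44.

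Allowing also for a baseline effect and a control response of 30-50%, the figures are 2.44, 2.34-2.36 and 2.19-2.23 for CKD odds ratios of 0.5, 0.33 and 0.2. Simulated power at 130 patients and 40% control response goes from 67.3% to 66.0%, 66.5% to 64.1% and 64.0% to 58.6% (SE 0.8 points). The significance verdict changes in 1.6%, 2.6% and 5.4% of trials.

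**6. Could the printed code be run as it stands?** Its contrast is on `treatment`, while MODEL holds `trt`, so the contrast names an effect that is not in the model. The reference level `Low` is also applied to CKD, which has no such level. The code must be rewritten, and SAP 9.7.1.2.2 supplies the terms.

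**The case for a change.** The best case for acting is that a pre-specified plan should allow one reading, and that a few words would achieve it. Section 10.2 is phrased as a commitment, the `region` legend shows it is not an isolated trace, and neither the pools nor the threshold for a separate large centre is fixed in the SAP. The disclaimer in SAP 10.3 covers wording and variable names; it does not obviously cover a model term that the text requires. A programmer making the smallest repair, changing `trt` to `treatment`, would still omit CKD.

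The factual part stands: the pooling has no assigned use, and the code does not match the text. The inference does not. Section 10.2 requires the pools to be fixed before database lock, which limits discretion over how they are formed, and a sentence that names no model cannot displace one stated five times. The minimal repair would leave CKD declared in CLASS with no function, against a text that names it explicitly for three endpoints and by reference for the fourth. The rest of SAP 10.3 also shows where this comes from: it announces MIXED above a logistic step, and refers to three treatment groups in a two-arm trial. That is carry-over from another plan and does not signal a second intended analysis.

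**Conclusion.** No change to the plan is needed. The centre-pooling paragraph and the `region` legend are most plausibly leftover template text, and the missing CKD term is a clerical fault in code that is declared illustrative. The governing text is complete for both the primary and the responder models, and analysts can work from it without guessing.

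The size of the matter supports this. A fixed model keeps its type I error with or without region (4.4-5.4%), and power differs by a few points at most. Leaving out CKD would shift the odds ratio toward 1 and cost between 1.3 and 5.4 points of power, with no added false-positive risk. These figures rest on assumed region counts, region variation, response rates, baseline effect and CKD effects, and they describe analyses that nobody is instructed to run. The largest come from the most extreme of those assumptions. Tidying the wording would change no planned result. The conclusion would differ only if 10.2 were read as overriding the stated primary model, and nothing in the protocol or SAP supports that reading.

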10.3 Sample SAS program for efficacy analyses

The SAS code provided is intended to reflect the type of analyses planned; however, the actual code used may not be a verbatim of this example. The variable names used in this code were selected for understanding of the methodology and do not necessarily reflect the actual variable names in the data.

ANCOVA model for primary analysis

For the ANCOVA model in the analysis of change from baseline in MSBP at Week 6, the following SAS code are used:

```
PROC MIXED DATA=eff;
  CLASS treatment CKD;
  WHERE population = population (FAS);
  MODEL response= treatment CKD baseline_MSBP;
  ESTIMATE 'Valsartan High dose vs. Valsartan Low dose' treatment 1 -1/CL;
  run;
```

- “eff” denotes the efficacy data set containing individual observations for the change from baseline in MSBP
- “treatment” denotes the variable containing the treatment groups (Low, High)
- “CKD” denotes the variable containing the CKD strata (CKD and non-CKD)
- “baseline_MSBP” denotes the centered baseline variable containing individual patient baseline MSBP deviation from the mean of all FAS patients.

Logistic regression model

The SAS procedure MIXED is used with the following SAS code:

```
proc logistic data=eff;
  class treatment CKD/(param=ref ref='Low');
  model response = trt base;
  contrast 'High dose vs. Low dose' treatment 1 -1 / estimate=exp;
run;
```

where `y`, `region`, `trt`, and `base` denote control or response variable, region, treatment, and baseline value (msSBP, or msDBP for `y` involving only msDBP) respectively.

The odds ratio of High dose /Low dose will be computed, along with associated 95% confidence intervals.

Comparability of baseline characteristics

Baseline comparability between the three treatment groups, for continuous parameters, was tested using two-sample t-test:

```
proc ttest;  
  class treatment;  
  variable <Quantitative baseline variable>;  
run;
```

Baseline comparability between treatment groups, for categorical parameters, was tested using a CMH chi square-test:

```
proc freq ;  
  tables treatment* <Qualitative baseline variable > / cmh noprint;  
  output out=<output dataset> cmhga;  
run;
```
